3.3.6 Protocol for blood tests (genomic and hormonal blood tests)

Genetic risk factors are reported to play an important role in the aetiology of varicose veins. In this proposed study, we aim to estimate the heritability of varicose veins among recruited pregnant women by taking a 30-ml blood sample for genomic DNA testing. This will be performed once in the first trimester. Results will be entered to the research database for analysis and correlation with the UK bio bank study (Fukaya *et al.*, 2018).

Along with the genomic blood samples, hormonal blood samples will be taken from patients in each trimester and three months after giving birth. This is because elevated estrogen and progesterone hormones levels were linked to VV development (Mashiah *et al.*, 1991; Ortega, Asunsolo, Leal, *et al.*, 2018). Progesterone serum blood test will be conducted to evaluate the progesterone levels during pregnancy and correlate the result with the incidence of VV. Normal progesterone serum levels varies according to the trimester of pregnancy. For instance, according to the NHS, progesterone levels in the first trimester estimates between 6.9 to 470 nmol/L, 71.6 to 300 nmol/L in the second trimester and 88 to 770 nmol/L in the third trimester. Therefore, progesterone hormone reaches the highest levels in the third trimester which suggests the potential effect of this hormone on venous pathology in late pregnancy.

In addition, estrogen hormone blood test will be tested to associate the effect of estrogen with VV incidence. Estrogen hormone has three main types which are estrone, estradiol and Estriol and each type has different function. Estrone (E1) is the main hormone in females which is found after menopause. Estradiol (E2) is a female hormone found in non-pregnant women and involved in regulating menstrual cycles. Estriol (E3) is a type of estrogen hormone produced with higher amounts in pregnancy. This proposed study will investigate Estriol (E3) and progesterone serum blood test in each follow up which include first, second, third trimesters and three months after

giving birth in order to correlate hormonal changes with any potential venous pathology incidence.

Therefore, four appointments will be arranged for each patient to investigate DNA genomic testing and Estriol (E3) and progesterone hormonal testing. First appointment during first trimester will include both genomic DNA and hormonal blood tests. The three remaining appointments in the second trimester, third trimester and three months after giving birth will include hormonal blood samples only. At the end of the study, these samples will be transferred to research tissue bank to store for future research.

3.3.7 Protocol for Quality of life assessment

Several quality assessment tools are used to measure the functional impact of a disease on patients' quality of life as perceived by the patient. Both generic and disease specific measures tools are used to estimate patient's quality of life status. This proposed study will use the Aberdeen Varicose Veins Questionnaire (AVVQ) quality of life assessment tool. AVVQ is a disease specific quality of life assessment tool which is developed in specific for patients with VV. Patients will be asked to answer 13 questions which assess patient symptoms such as pain, swelling, itching and ulcers. This tool also assesses the impact of VV on social and daily life activities and the use of support stocking. Perceived cosmetic impact is taken into consideration in AVVQ tool. Each question is designed to reflect the severity of the issue referred to in the question. AVVQ questionnaire is scored from 0-100, where 100 represents the most severe issues related to VV and lowest quality of life while zero represents the best quality of life. Finally, patients will be thanked for their participation and excused.

3.4 Clinical intervention and procedures

Clinical intervention and procedure	Time

 • Consent • Clinical data collection • Blood samples (genomic+ hormonal) • DUS • VFI • Truncated cone tool • PPG • AVVQ 	First trimester (0-13 weeks)

 • Clinical data collection • Blood sample (hormonal only) • DUS • VFI • Truncated cone tool • PPG • AVVQ 	Second trimester (14-26 weeks)

 • Same as second trimester 	Third trimester (27-40 weeks)

 • Same as second trimester 	Three months after giving birth

4 Participant entry

4.1 Pre-registration evaluation

Blood test for pregnancy conformation.

4.2 Inclusion criteria

- Pregnant women who are aged between 18 to 47 years old
- Patients who are willing to be followed up for 1 year and agreeing to give the informed consent will be included in the inclusion criteria.

4.3 Exclusion criteria

- Any incomplete cases such as intrauterine death.
- Participants who fail to attend the scans after their first visit will be excluded.
- Patients with congenital vascular abnormalities/syndromes such as Klippel Klippel-Trenaunay syndrome.
- Patients who are unable to provide consent.
- Anyone who are taking part in any other research.
- Potential participants who might not adequately understand verbal explanations or written information given in English, or who have special communication needs.
- Patients with signs of acute deep vein thrombosis.
- Patient suffered from severe injury of their great-saphenous vein.

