4.5 Withdrawal criteria

Participants choice

5 Adverse events

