5.2.2 Serious AEs

An SAE form should be completed and faxed to the Chief Investigator within 24 hours. However, death due to eclampsia and any health complications worsened during pregnancy does not need reporting as SAEs.

All SAEs should be reported to **the North of Scotland Research Ethics Committee** where in the opinion of the Chief Investigator, the event was:

- 'related', ie resulted from the administration of any of the research procedures; and

- 'unexpected', ie an event that is not listed in the protocol as an expected occurrence

Reports of related and unexpected SAEs should be submitted within 15 days of the Chief Investigator becoming aware of the event, using the NRES SAE form for non-IMP studies. The Chief Investigator must also notify the Sponsor of all SAEs.

Local investigators should report any SAEs as required by their Local Research Ethics Committee, Sponsor and/or Research & Development Office.

Contact details for reporting SAEs

[contact]

[contact]

[contact] attention [name]

[contact] (Mon to Fri 09.00 – 17.00)

6 Incidental findings:

A lay summary of aggregated results will be provided to all participants. If there is an incidental finding such as DVT, which likely have a major impact on patient's medical management then the doctor treating her will be informed and participant will be removed/ withdrawn from the study.

7 Assessment and follow up

All previously mentioned interventions and procedures including (DUS, VFI, Truncated cone tool, PPG, hormonal blood test, AVVQ questionnaire) will be performed four times (in first, second, third trimester once and three months after giving birth). DNA genomic blood test will be performed once only in the first trimester of pregnancy. No

further follow-up required after this time point. The study expected time for each participant is 12 months in total.

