8.2 Analysis plan

All analyses will be performed based on the intention of follow-up. The analysis population will include all participants enrolled in the study, including those who developed varicose veins during pregnancy and those who do not.

Analysis of primary and secondary outcomes:

Venous patency and Peak reflux time recordings from VFI scan will be correlated with Venous patency and peak reflux time recordings from DUS scan. This will be performed using descriptive summary statistics. Mixed multivariable logistic regression will be used to model venous patency and peak reflux velocity in each scan.

Secondary outcome which include measuring the circumferences (C1, C2) and length of segments (h) using Truncated cone method. Calculated volume will be determined by summing segment volumes derived from the truncated cone formula. Pearson product moment correlations, paired t tests, and linear regression tests will be used to assess relative association and absolute differences between calculated volumes in each follow up.

Secondary outcome which include PPG will be analysed by comparing the mean value for the venous refilling time (VRT) by Student's *t* test, agreement between DUS and PPG classification was expressed as a kappa (**K**) value.

Genomic DNA blood samples results will be correlated with the UK biobank study. Test statistics will be used to identify genetic variants that influence varicose vein susceptibility.

Each hormonal blood samples results including Estroil (E3) and progesterone serum levels will be correlated with the results of the next follow up to provide comprehensive information about increased hormonal levels in pregnancy and varicose veins development.

Outcome of quality of life statistical analysis will be performed using the Statistical Package for the Social Sciences (SPSS 23.0) for Windows. Evaluation of AVVQ consisted of quality of life in first trimester, second trimester, third trimester and three months after giving birth will be done using the Friedman test.

8.3 Data analysis:

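### Sections 4.3 and 6 exclude or remove women for events after entry, section 8.2 analyses all enrolled, and no passage says which rule sets the analysis population

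*Combined protocol and SAP*

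**What the plan says.** Section 4.3, under participant entry, includes two criteria that are not purely entry conditions: "Participants who fail to attend the scans after their first visit will be excluded" and "Any incomplete cases such as intrauterine death". It also has a criterion that can be checked at entry, "Patients with signs of acute deep vein thrombosis".

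Section 6 deals with incidental findings likely to have a major effect on a woman's medical management, with DVT as the example. The treating doctor is told and the "participant will be removed/ withdrawn from the study".

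Section 4.5 gives one withdrawal criterion, "Participants choice", and mentions none of these removals.

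Section 8.2 opens with "All analyses will be performed based on the intention of follow-up", a principle it does not define, and continues "The analysis population will include all participants enrolled in the study", whether or not they develop varicose veins (VV). Section 9.2 keeps women in follow-up and analysis in one stated case, when a clinician gives alternative treatment. It does not cover missed scans, pregnancy loss or DVT. Section 3.2 requires storage of data for at least 10 years, which concerns archiving and not use in analysis.

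**The concern.** An exclusion criterion normally decides who may enter. A criterion met by not turning up later decides who stays, and if it carries over to the dataset it decides who is counted. Section 8.2 counts everyone enrolled. The text does not say whether a woman excluded under 4.3, or removed under 6, leaves the study procedures only or the analysis as well.

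The choice matters because the post-entry events may be related to what is being studied. Section 7.2 makes patency on duplex ultrasound (DUS) a primary outcome, and section 3.3.2 assesses it by compressing the veins to rule out clot. Removing the data of a woman with a DVT would therefore select on something close to a primary outcome. Dropping women for missed scans would also discard scans they did attend. Depending on the reading, these could include third-trimester scans, when section 8.3 compares women with and without VV, and post-partum scans, the time point of the primary objective in section 2.

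**Working it through.** **The passages side by side**

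- Missed scans after the first visit: 4.3 excludes; 8.2 includes. Section 3.2 requires consent before any study procedure, so a woman who has had a first visit is already enrolled.
- Incomplete cases such as intrauterine death: 4.3 excludes; 8.2 includes if the woman was enrolled. Section 3.4 places entry at 0-13 weeks, so a loss could be found at entry or occur later. The documents give no split.
- Incidental finding such as DVT: 6 removes; 8.2 includes. Section 3.3.2 has any thrombus recorded and the recordings entered in the database for analysis.
- Precedence, and the fate of data already collected: not stated for any of the three.

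**The plan's own figure.** Section 8.1 states 91.27% power for n = 70, proportions 0.25 and 0.10, two-sided 5% exact binomial test. This reproduces: reject if X ≤ 10 or X ≥ 26, actual size 0.0383, power 0.9127. It uses all 70 women.

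**Illustration of what is discarded if 4.3 is applied to the analysis**

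Inputs: N = 70 (8.1) and four visits per woman (3.1). The documents give no rate of missed visits, so m = 5% or 10% is an assumption; p = 1 − m. Only attended visits are counted, because no rule can recover a scan that was not done.

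- (A) Any missed scan excludes; each of the three later visits is missed independently with probability m. Excluded 70(1 − p³); attended 70(1 + 3p); kept 4 × 70p³. Third-trimester scans attended 70p, discarded 70p(1 − p²); the same for post-partum scans.
- (B) Any missed scan excludes; women drop out for good, with probability m before each later visit. Excluded and kept as in (A); attended 70(1 + p + p² + p³). Third-trimester scans attended 70p², discarded 70p²m. No post-partum scan is discarded, since anyone who attends that visit attended all.
- (C) Only women who never return are excluded; here m is the share of women who attend visit 1 only, and the rest attend everything. Attended 70(4 − 3m); discarded 70m first-trimester visits.

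| Reading | m | Women excluded | Visits attended | Attended visits discarded | Third-trimester discarded | Post-partum discarded |
|---|---|---|---|---|---|---|
| A | 5% | 10.0 | 269.5 | 269.5 − 240.1 = 29.4 (10.9%) | 6.5 of 66.5 | 6.5 of 66.5 |
| A | 10% | 19.0 | 259.0 | 259.0 − 204.1 = 54.9 (21.2%) | 12.0 of 63.0 | 12.0 of 63.0 |
| B | 5% | 10.0 | 259.7 | 259.7 − 240.1 = 19.6 (7.6%) | 3.2 of 63.2 | 0 |
| B | 10% | 19.0 | 240.7 | 240.7 − 204.1 = 36.6 (15.2%) | 5.7 of 56.7 | 0 |
| C | 5% | 3.5 | 269.5 | 3.5 (1.3%) | 0 | 0 |
| C | 10% | 7.0 | 259.0 | 7.0 (2.7%) | 0 | 0 |

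The table covers missed visits only. DVT and pregnancy loss are not modelled, because the documents give no frequency for either.

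**The case against.** The best defence is that the passages can be reconciled on an ordinary reading. Section 8.2 alone names an analysis population; 4.3 sits under participant entry; and leaving the study, in section 6, describes participation and not a dataset. The recording rules in 3.3.2 point the same way. If 8.2 governs, there is one rule and nothing collected is lost. This reading is reasonable and may be what was meant. It does not settle the matter, because 4.3 gives its exclusion no scope, no sentence ranks the sections, and 9.2 spells out retention for a different case only.

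Second, 4.3 speaks of scans in the plural, which favours reading (C), where the loss is small and no later scan is affected. That is fair, and it is why the table must not be read as a forecast. But the sentence can also bear (A) or (B).

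Third, for women who leave by choice, the terms on data use may stand in consent documents that are not part of the text reviewed. No gap is alleged there.

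Three stronger inferences are tempting and unsupported:

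- That the plan discards these women's data, or that VV frequency is biased in a known direction. The text does not say the first, and nothing in it gives a direction or size for the second.
- That the exclusions reduce the power in 8.1 by a stated amount. Section 8.1 does not say which event its proportions describe, and no exclusion rate is given.
- That the mixed model in 8.2 is confined to single visits. Its reference to each scan follows a comparison of DUS with vector flow imaging (VFI) and more naturally means the type of scan. It leaves open which visits are used.

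**Conclusion.** The point holds as an unresolved conflict over who is analysed, and it should be settled before analysis. It rests on the wording alone: one exclusion in 4.3 can be met only after enrolment, another can be, section 6 adds a third route out, and 8.2 includes everyone enrolled without any rule of precedence. The harm is conditional on 4.3 or 6 being carried into the analysis. If so, the cohort is selected on post-entry events that may relate to venous outcomes, and the loss of attended visits could lie anywhere from about 1-3% under (C) to about 11-21% under (A), given assumed rates of 5% or 10%. That spread shows that the scope of one sentence matters; it does not estimate what will happen in this study.

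**What to change.** - Limit 4.3 to criteria that can be assessed at entry. Move missed scans and pregnancy loss after entry to a list of reasons for incomplete follow-up.
- Reconcile 4.3, 4.5 and 6 with 8.2 by stating that the end of study procedures does not remove a woman from the analysis.
- State in 8.2 that all enrolled eligible women are analysed with all data from attended visits. This includes any thrombus recorded on a study scan after eligibility is confirmed. Make it subject to the consent terms for women who withdraw by choice.
- State that the mixed model in 8.2 and the longitudinal analysis in 8.3, both already planned, use all attended visits.
- Add one sensitivity analysis for informative loss, at the post-partum visit as well as the final trimester. Recalculate VV frequency over a range of assumed risks in unscanned women, with the range fixed in advance.

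The cost is protocol and SAP wording and one extra analysis, with no added visits or participants. The downside is that some women contribute incomplete series and the models rely on data being missing at random, which the sensitivity analysis must probe. Outcomes at visits never attended cannot be restored. Clinical management after a DVT is outside this point.

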4.4 Recruitment and follow up period

Recruitment period will take up to three months. Follow up period will be conducted at the end of first, second and third trimester and three months after giving birth.

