Outcome measures: Venous patency, blood flow direction, peak reflux velocity, circumferences (C1, C2) at the end of each segment length (L), BMI, VRT, Genomic DNA blood test, Estriol (E3) levels, progesterone serum levels, outcome of quality of life.

Population: 70 Random pregnant women.

Eligibility: Pregnant women aged between 18-47 years old.

Duration: 1 year, follow up period will be conducted at the end of first, second and third trimester and three months after giving birth.

1 Introduction

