1.2 Rationale for current study

Regardless of the underlying pathophysiological cause, VV may have a negative social impact on patient's life and negative economic impact on health care budget. VV if left untreated can progress to late stages of chronic venous insufficiency (CVI) which include skin changes and ulceration (Adhikari *et al.*, 2000). Ulcers lower patient's quality of life and may result in social isolation, depression, reduce the ability to work and patients will be dependent on others (Evans *et al.*, 1994; Cesarone *et al.*, 2002). Furthermore, venous disease is costly to manage for healthcare service. For example, the cost of managing chronic wounds caused by ulcers in the UK National Health Service (NHS) during 2005 to 2006 was estimated from 2.3 to 3.1 billion pounds which was equivalent to 3% of total UK health care budget (Posnett, J. and Franks, 2007). Interestingly, the cost was increased between 2012 to 2013 when cost was estimated at 5.3 billions of pounds annually which consume 4% of the total health UK health care budget (Guest *et al.*, 2015).

1.3 Research hypothesis:

The development of post-partum chronic venous insufficiency is predictable and caused by both mechanical and hormonal factors.

2 Study aim and objectives:

The primary aim of this proposed study is to better understand the pathophysiology of VV in pregnant women. This aim will be achieved by meeting the following objectives:

Primary objective:

To develop an antenatal test to predict the risk of developing VV post-partum.

Secondary aims:

1. To evaluate mechanical factors causing VV in pregnancy
2. To evaluate hormonal factors causing VV in pregnancy.
3. To determine whether lower limb pain during pregnancy is related to changes in lower limb venous system.

3 Methods

3.1 Study design:

A prospective longitudinal study will be undertaken to assess the development of VV among pregnant women. This study will follow up patients for one year, starting by following up pregnant women from the first trimester of pregnancy to the end of the second and third trimester. Last follow up will be performed three months after giving birth. Consequently, this proposed prospective study will be conducting four follow ups for each participant.

3.2 Recruiting pregnant women in their first trimester:

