The data obtained will be subjected to statistical analysis by an independent biostatistician. SPSS Version 23.0 or/ and STATA Version 10.0 will be used for statistical analysis. Measures such as the mean and standard deviation or median and interquartile range will be used to summarise continuous variables such as age and BMI. Tables reporting the numbers and percentages will be used for categorical variables such as varicose veins and smoking. Chi square or Fisher's exact test will be used to compare categorical variables such as varicose veins and smoking at the final trimester. The t-test or Mann-Whitney test will be used to compare continuous variables such as age with varicose veins at the final trimester. The paired t-test or Wilcoxon signed-rank test will be used to compare BMI between first and third trimester. The Kappa statistic will be used to compare DUS and VFI regarding direction and velocity. Longitudinal analysis will be used to look at factors associated with varicose veins. Factors include age, BMI, smoking, ethnicity, pregnancies and family history. A significance value (p-value) less than 0.05 is considered statistically significant.

9 Regulatory issues

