Some pregnant women may experience complications during pregnancy. These complications may affect the mother's health or fetal health or both. The most common pregnancy complications include high blood pressure, gestational diabetes, preeclampsia placenta previa and infections. Pregnancy complications will be recorded in this study for each participant in order to correlate any potential complication with the incidence of VV and to generate comprehensive analysis at the end of this study.

Preeclampsia is one of the main pregnancy complications which cause fetal morbidity and mortality. Early signs of preeclampsia include high blood pressure and accumulated amounts of proteins in urine which is known as proteinuria after 20 weeks of pregnancy (Oettinger-Barak *et al.*, 2005). Untreated preeclampsia may lead to eclampsia which involves seizures that may result in coma, brain damage and fetal death. Preeclampsia is aggravated by several risk factors including older age, nulliparous, chronic hypertension, high BMI>30 and gestational diabetes during pregnancy.

High blood pressure and Gestational diabetes mellitus (GDM) are serious pregnancy which result in maternal and fetal complications. Hypertension arises when arteries carrying blood from the heart to body organs are narrowed which thus cause high blood pressure in arteries. In pregnancy, hypertension reduce amount of blood flow containing nutrition and oxygen to the placenta. Consequently, this will affect fetal growth and further complications such as preterm delivery and preeclampsia. On the other hand, GDM is identified as glucose intolerance developed during pregnancy

period at any grade and whether insulin or diet adjustment is used for treatment (Spaight *et al.*, 2016). Pregnant women with GDM are at higher risk of developing diabetic 2 after pregnancy (Berger *et al.*, 2016). Furthermore, GDM is coupled with high rates of caesarean delivery, increased obesity, fetal macrosomia which may cause birth complications such as stillbirth and shoulder dystocia (Lefkovits, Stewart and Murphy, 2019).

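### The third-trimester visit has no single stated timing, and no rule covers a woman who delivers before it

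*Combined protocol and SAP*

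**What the plan says.** **Timing at the end of the trimester.** Section 4.4 states "Follow up period will be conducted at the end of first, second and third trimester and three months after giving birth". The Study summary has the same sentence, and section 3.1 describes follow-up "from the first trimester of pregnancy to the end of the second and third trimester".

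**Timing anywhere in the trimester.** The procedures table in 3.4 lists the visit against "Third trimester (27-40 weeks". Section 7 says the assessments "will be performed four times (in first, second, third trimester once and three months after giving birth". Sections 3.2 and 3.3.6 place the blood-test appointments simply in the third trimester.

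**Missed scans.** Section 4.3 says "Participants who fail to attend the scans after their first visit will be excluded". Section 8.2 says that all enrolled participants are analysed. No passage deals with a woman who delivers before the third visit, and no missing-data method is given.

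**Analyses that use the visit.** Section 8.3 will "compare categorical variables such as varicose veins and smoking at the final trimester", compare continuous variables such as age by VV status at the same point, and run a paired comparison of BMI between the first and third trimesters. Section 8.2 applies a Friedman test to AVVQ over the four visits and correlates each hormone result with the next follow-up. Section 3.2 records fetal weight in the second and third trimesters only.

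**Complications.** Appendix 13.1 says "Pregnancy complications will be recorded in this study for each participant in order to correlate any potential complication with the incidence of VV". It links hypertension to preterm delivery, placenta previa to premature delivery, and infection to preterm labour.

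**The concern.** A site that follows 4.4 would book the third visit near term. A woman who delivers before that date cannot have it: her pregnancy is over, so her third-trimester scan, hormone sample, AVVQ and fetal weight do not exist. She then cannot enter the final-trimester VV tests or the paired BMI test.

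By the plan's own appendix, the women likeliest to be lost this way include those with hypertension, placenta previa or infection, which are among the complications the study wants to relate to VV. If VV risk also differs by those complications or by time to delivery, the women still pregnant at the visit do not represent the cohort.

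Section 4.3 adds a second risk. If an early deliverer counts as someone who failed to attend, she could also lose her three-month post-partum assessment. That assessment serves the primary objective, which is to predict VV post-partum.

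**Working it through.** **1. The plan's own figure.** Section 8.1 gives 91.27% power for an exact two-sided 5% binomial test of 0.25 against 0.10 with 70 women. With at most 2.5% in each tail, the test rejects if X ≤ 10 or X ≥ 26. At 0.10, P(X ≤ 10) + P(X ≥ 26) = 0.9127, so the figure reproduces. Section 8.1 does not say which visit the proportion refers to and states no allowance for missed visits.

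**2. Where the visit falls.** The Study summary, 3.1 and 4.4 say the end of the trimester, which is week 40 by the table in 3.4. The same table, section 7, 3.2 and 3.3.6 say only the third trimester. Both readings are live, and no target week is set.

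**3. Share delivered before the visit.** The documents give no distribution of gestation at delivery. Assumption: normal, mean 39.0 to 40.0 weeks, SD 1.5 to 2.0. The share lost is Φ((visit week − mean)/SD), and the number lost is that share × 70.

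| Visit at week | Lowest share | Highest share | Women of 70 |
|---|---|---|---|
| 40 | Φ((40−40)/1.5 or 2.0) = 0.50 | Φ((40−39)/1.5) = 0.75 | 35 to 52 |
| 38 | Φ((38−40)/1.5) = 0.09 | Φ((38−39)/2.0) = 0.31 | 6 to 22 |
| 36 | Φ((36−40)/1.5) = 0.004 | Φ((36−39)/2.0) = 0.067 | 0 to 5 |

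The visit week drives the loss far more than the assumed mean and SD do. The cut-offs are exact weeks. If a window ran through the last day of week 36, to 37.0 weeks, a woman booked on that last day would face Φ((37−40)/1.5) = 0.02 to Φ((37−39)/2.0) = 0.16.

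**4. What selective loss could do (assumed illustration).** Take 70 women with true VV of 25%: 17.5 with VV and 52.5 without.

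- Equal loss of 30%: 12.25 / (12.25 + 36.75) = 25.0%. Precision falls, but there is no bias in the proportion.
- Loss of 50% with VV and 30% without: 8.75 / (8.75 + 36.75) = 19.2%, in about 46 women.

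Nothing in the documents says which pattern applies.

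**5. Other analyses touched.** The Friedman test needs all four AVVQ values, so a missed third visit removes the woman. The hormone plan has three links between successive visits, and a missing third visit breaks two of them (second to third, and third to post-partum).

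**The case against.** The strongest reply is that the operational table permits any week from 27, and section 7 asks only for one assessment in the trimester. A team working from these would see most women well before delivery. At week 36 the assumed loss is 0 to 5 women. This stands: the large loss belongs to one reading of the timing. It does not dispose of the point, because three statements say the end of the trimester and the plan never chooses between the readings.

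A reader might go further in four ways that the documents do not support:

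- **That the complication–VV correlation depends on this visit.** Appendix 13.1 speaks of VV incidence and names no visit. Section 8.3 also plans a longitudinal analysis that is not confined to the final trimester. Early deliverers can still supply first-trimester, second-trimester and post-partum scans, if 4.3 does not remove them.
- **That bias is established.** No passage relates delivery timing to VV. If the two are unrelated, the loss costs precision only.
- **That gestational diabetes or fetal size adds to the selection.** The appendix ties gestational diabetes to caesarean rates, not to earlier delivery, and says nothing on fetal size and timing.
- **That 4.3 certainly excludes early deliverers.** It can be read as covering only women who never return after visit one, and 8.2 analyses everyone enrolled. The two sections need reconciling; neither settles the matter alone.

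**Conclusion.** The defect is unreconciled timing of the third assessment, with no rule for a woman who delivers before it. On the end-of-trimester wording, early deliverers drop out of the final-trimester VV tests and the first-versus-third-trimester BMI test. Appendix 13.1 implies that this loss is selective for hypertension, placenta previa and infection. Those comparisons may therefore be biased; the documents do not show that they are.

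It would be tempting to conclude that the visit falls after most women have given birth. That holds only if the visit is at week 40 and the assumed delivery distribution is right (50–75%). The same assumptions give 9–31% at week 38 and 0.4–7% at week 36. The size is therefore a range set mainly by a visit week that the plan leaves open.

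The point is worth acting on before recruitment because the correction is cheap and a missed third-trimester visit cannot be recovered afterwards.

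**What to change.** 1. Replace the timing statements in the Study summary, 3.1, 3.2, 3.3.6, 3.4, 4.4 and 7 with one third-trimester research-visit window. Keep it inside the table's 27–40 weeks and close it before term, for example by the end of week 36. State the closing day exactly, because step 3 of the working shows that one week matters.
2. Book the research visit earlier in the window when an earlier delivery is already planned. This moves a study assessment only and leaves clinical care unchanged.
3. Record gestational age at the visit and at delivery.
4. Amend 4.3, consistently with 8.2, so that women who deliver before the visit stay in the study for the three-month post-partum scan and in the analysis.
5. Report missed third-trimester visits by complication status.

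Cost: scheduling text, one line in 4.3, two recorded dates or gestational ages, and one table. No visit is added. The downside is that the last weeks of pregnancy, when mechanical load may be greatest, are not observed.
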